Our proposed study is a prospective single arm study, which will aim in an exploratory/pilot fashion to assess the following variables in a population of patients with cancer with prior vaccination against COVID-19.

- To study the difference in mean titers for SARS-CoV-2 spike IgG in patients with cancer after administering an additional (fourth) booster dose of the BNT162b2 vaccine in patients that had a poor serological response after standard homologous (BNT162b2 → BNT162b2) vs. heterologous (mRNA-1273 → BNT162b2) vaccine series (including a third dose).
- To study safety and side effects from an additional booster dose of the BNT162b2 COVID vaccine

Inclusion criteria:

Our target population consists of patients with a known or previous diagnosis of cancer who had received three prior doses of one of the mRNA based COVID-19 vaccines including a booster dose. Our study will employ the following inclusion criteria:

- Above the age of 18
- Have a diagnosis of prior or active malignancy- either hematological or solid tumor
- Have a negative or low-level SARS-CoV-2 spike IgG after at least 14 days of booster vaccination series irrespective of active/inactive cancer status, on observation, or active therapy.
- Have received an FDA authorized booster dose of mRNA (BNT162b2 or mRNA 1273) vaccine at least 28 days before study enrollment

- Decline to participate in cohort 2 requiring randomization of BNT162b2 and Ad26.CoV2.S vaccines

Exclusion Criteria

- Patients who have had a serious adverse reaction to any prior COVID-19 vaccines resulting in emergency room visit or hospitalization, had events related to myocarditis, thrombosis and thrombocytopenia syndrome or anaphylaxis to any prior dose of the COVID-19 vaccines.
- Patients who have had a documented COVID-19 infection in the 90 days prior to study enrollment

Outcomes

Primary outcome: To compare the increase in mean titers for SARS-CoV-2 spike antibody after 4 weeks following a homologous (BNT162b2 → BNT162b2) vs. heterologous (mRNA-1273 → BNT162b2) additional booster dose of COVID vaccine in patients that had a poor serological response after standard vaccine series (including a third dose).

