Cohort 1. For a 1 sample test of proportions our hypothesis is that booster vaccine dosing will induce detectable immunity by the spike IgG assay in at least 20% of individuals. Null hypothesis is a positivity rate of 10% to account for some test variability and therefore the alternative hypothesis is $p > 30\%$. Our planned sample size of up to 250 will have ample power ($>95\%$) to detect such a difference in our primary endpoint and will still retain 80% power and 5% significance in the secondary preplanned subset analyses as long as cohort sizes per subset are >26 . We anticipate the large majority of patients will be hematologic malignancy patients and such preplanned subset analyses will include two cohorts, the highly immune suppressed (prior anti- CD20, CAR-T, or SCT therapy), and all others (solid tumor/hematologic malignancy patients) who do not fall into the first cohort. We anticipate cohort sizes of at least 26 per cohort based on the numbers of seronegative patients identified in our prior study.

Cohort 2. Our null hypothesis is that the additional homologous booster vaccine dosing will induce detectable immunity (positive spike IgG test result higher than the predefined threshold for seropositivity—i.e. >1000 AU/ml) by the spike IgG assay in at least 25% of individuals. Alternate hypothesis is that heterologous vaccination with the AdCov2.S vaccine will increase this seroconversion rate by an additional 25%- that is to 50%. With an alpha of 0.05 and 80% power to detect the difference, we would require a sample size of 46 in each group. Accounting for 5% dropout rate, we will thus use a planned sample size of up to 100 subjects. We anticipate the large majority of patients will be hematologic malignancy patients and such preplanned subset analyses will include two cohorts, the highly immune suppressed (prior anti-CD20, CAR-T, or SCT therapy), and all others (solid tumor/hematologic malignancy patients) who do not fall into the first cohort.

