Cohort 3. Our null hypothesis is that the additional homologous booster vaccine dosing with the BNT162b2 after prior BNT162b2 vaccination will increase mean titers in the spike IgG assay by at least 300%. Alternate hypothesis is that heterologous vaccination with the BNT162b2 after prior mRNA-1273 vaccination will increase mean titers by an additional 300%- that is to 600%. To achieve 80% power at a significance level alpha = 0.05, a one sided two sample t-test would require 22 samples per group to detect differences in mean titers of 750 AU/mL and 1500 AU/mL at an estimated standard deviation of 1000 AU/mL. Given we estimate 30-40% patients with have had prior mRNA-1273 vaccination and accounting for 5% dropout rate, we will thus use a planned sample size of 80.

Statistical analysis

To assess our goals as outlined above, statistical analysis will be done in the R software environment. The primary aim of cohorts 1 and 2 examining the seroconversion rates after 4 weeks will be checked with a one sample z test of proportions. The primary aim of cohort 3 examining the increase in mean Spike IgG titers will be checked with a one sided two sample t-test. Secondary aims involving the significance of associations between certain malignancies and the rates of seroconversion in our prospective single arm study will be measured by Fisher's exact and Cochran- Mantel-Haenszel tests depending on if analysis is conducted by a stratified variable (Cochran- Mantel-Haenszel) or not (Fisher's exact). The more complicated relationship between patients' seroconversion rates, their recent receipt of medical treatment, and additional factors such as history of malignancy will be examined through a multivariate logistic

regression model. After addressing the appropriateness of interaction terms, a Wald test will be used to consider the statistical significance of all included variables at the $p < 0.05$ level.

Duration

Our study will follow patients from Aug 1, 2021 through November 2023, which will allow for sufficient time to assess follow-up serologies after COVID-19 vaccination infection in patients with cancer (24 months follow up).

Matching

Cohort 1

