Patients would serve as their own control. Baseline seropositivity rate by definition is 0% for the cohort but anticipating natural and laboratory variation we have based on statistical null hypothesis around a 10% seropositivity rate at 4 weeks and anticipate that booster vaccination will increase this to higher than 30%.

Planned intervention

Cohort 1

The planned intervention is to administer a booster dose of the BNT162b2 (Pfizer/BioNTech) or mRNA-1273 (Moderna) vaccine to patients that meet FDA/CDC criteria of cancer on active therapy or patients that have received a stem cell transplantation or CAR-T cell therapy in the last 2 years or those that have a negative spike IgG after having = completed one of the FDA's Emergency Use Authorized vaccination series for COVID-19 (i.e. 2 doses of the mRNA-based mRNA-1273 (Moderna), BNT162b2 (Pfizer/BioNTech), or a single dose of the adenovirus-based Ad26.COV2.S (Johnson & Johnson) vaccine, following completion of their vaccination series.

Cohort 2

The planned intervention is to administer an additional booster dose of the BNT162b2 (Pfizer/BioNTech) or Ad26.COV2.S (Johnson & Johnson) vaccine to patients that meet eligibility criteria for cohort 2 in a 1:1 randomization fashion with negative spike antibody vs. low positive antibody level serving as a stratification factor to ensure controlling for key confounder.

Cohort 3

The planned intervention is to administer an additional booster dose of the BNT162b2 (Pfizer/BioNTech) vaccine to patients that meet eligibility criteria for cohort 3 in a prospective single arm fashion in patients that had a poor serological response after standard vaccine series (including a third dose).

Participant recruitment

The study will both utilize data from the electronic health record to identify patients meeting the above inclusion criteria and enroll them on to the study and accept patients self-referred or referred by their provider at Montefiore Medical Center or external institutions. A consenting visit will be scheduled with each prospective patient. Following a carefully conducted and documented informed consent process subjects who consent for study participation will then be screened. Patients who qualify for booster COVID-19 vaccination as per FDA/CDC guidance and study criteria will then participate in our study.

Data and Safety Monitoring Plan

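### Cohort 3's primary test compares non-randomised prior-vaccine groups on an increase whose scale is not fixed, without baseline spike IgG as a covariate or stratum

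*Combined protocol and SAP*

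**What the plan says.** All references are to the combined protocol and SAP.

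- **Test** (Statistical analysis): "The primary aim of cohort 3 examining the increase in mean Spike IgG titers will be checked with a one sided two sample t-test". No covariate or stratum is named.
- **Outcome** (Cohort 3, Outcomes): "To compare the increase in mean titers for SARS-CoV-2 spike antibody after 4 weeks", homologous versus heterologous fourth dose. The text does not say whether the increase is a difference, a ratio or a comparison of 4-week means.
- **Sizing** (Sample size, Cohort 3): the homologous group's mean is taken to rise by at least 300%, and heterologous vaccination "will increase mean titers by an additional 300%- that is to 600" per cent. The calculation is then done in AU/mL: 22 per group "to detect differences in mean titers of 750 AU/mL and 1500 AU/mL at an estimated standard deviation of 1000 AU/mL".
- **Allocation** (Cohort 3): openly non-randomised and exploratory. Everyone receives BNT162b2, and the groups differ by earlier vaccine.
- **Baseline range** (Cohort 3, Inclusion criteria): "Have a negative or low-level SARS-CoV-2 spike IgG after at least 14 days of booster vaccination series". Low-level is given no number there. For cohort 2, Sample size defines success as a "positive spike IgG test result higher than the predefined threshold for seropositivity", put at more than 1000 AU/mL.
- **Baseline data** (Methods; Study calendar cohort 3): spike antibody is measured at screening and at the initial visit.
- **Cohort 2** (Planned intervention): randomisation uses "negative spike antibody vs. low positive antibody level serving as a stratification factor to ensure controlling for key confounder".
- **Only multivariable model** (Statistical analysis): a logistic model for the "relationship between patients' seroconversion rates, their recent receipt of medical treatment, and additional factors such as history of malignancy". It does not cover a titre outcome.

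**The concern.** Cohort 2 is randomised and still controls baseline antibody by design. Cohort 3 admits the same mix of negative and low-level patients and has no randomisation to balance them, yet its primary contrast has no such control.

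Analysing the increase removes a baseline imbalance only when the rise, on the scale analysed, does not depend on baseline. If titres tend to multiply, the group that starts higher gains more AU/mL with no benefit from switching. A baseline difference could then be read as success of switching or, in the other direction, could hide a real benefit. Because the scale of the increase is not fixed, the reader cannot tell which situation applies.

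**Working it through.** **1. The plan's own figure.** Difference 1500 - 750 = 750 AU/mL, SD 1000, one-sided alpha 0.05, power 80%:

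n per group = 2 × (1.645 + 0.842)² × (1000/750)² ≈ 22, as stated. (The exact t calculation gives 23.) With 30% prior mRNA-1273, 22/0.30 gives 74, and 74/0.95 gives 78, consistent with 80. The sample size is not at fault.

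**2. What the sizing implies about baseline.** If 750 and 1500 are increases, 750/3 = 250 and 1500/6 = 250 AU/mL, so equal baselines. If they are 4-week means, 750/4 = 187.5 and 1500/7 = 214. The text allows both readings.

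**3. Direction of the bias.** Let D be the baseline difference and b the within-group slope of 4-week titre on baseline. The AU/mL increase is biased by (b - 1) × D, which is zero if b = 1 or D = 0. With a rise of 300% in both groups and a homologous baseline of 250, the homologous group gains 3 × 250 = 750 AU/mL. At a baseline ratio of 1.25 the heterologous group gains 3 × 312.5 = 937.5, a spurious 187.5. At 1.5 it gains 3 × 375 = 1125, a spurious 375.

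**4. Size, by simulation (illustration only).** There were 20,000 trials per scenario and a one-sided 5% test. Group sizes were 53/23 or 46/30 (80 less 5% = 76, with 30% or 40% prior mRNA-1273). Titres were lognormal, with no true difference between groups. Baseline ratios and coefficients of variation (CV, the same for baseline and fold) are assumptions. A CV of 0.7 reproduces the plan's SD of about 1000; a CV of 1 gives about 1600.

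| How titres rise | Analysis | Error, ratio 1.25 | Error, ratio 1.5 |
|---|---|---|---|
| Proportional, CV 0.7 | t-test, AU/mL increase | 20% | 39-41% |
| Proportional, CV 1 | t-test, AU/mL increase | 14-15% | 25-26% |
| Proportional, either CV | t-test, fold rise | 5-6% | 5-6% |
| Proportional, either CV | ANCOVA, log scale | about 5% | about 5% |
| Independent of baseline (mean 750, SD 1000) | t-test, AU/mL increase | 5-6% | 5-6% |
| Independent of baseline | ANCOVA, log scale | about 5% | about 5% |

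A ratio of 2 gives 49-50% (CV 1) or 73-76% (CV 0.7) for the AU/mL t-test, but it is extreme given the entry criterion. Capping baselines at 1000 AU/mL (cohort 2's threshold, assumed here for cohort 3) shrinks it to 1.6-1.7, with error 37% or 62-65%.

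**5. Opposite direction.** With true rises of 300% and 600%, CV 0.7 and an AU/mL increase, t-test power is 77-80% at equal baselines and 42-44% at a ratio of 0.75. Log-scale ANCOVA holds 96-98% at both.

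**6. Limits of adjustment.** With assay error of log-SD 0.3 at both visits and proportional rises, log-scale ANCOVA error at ratios 1.25 and 1.5 is 6% and 7-8% (CV 1) or 8% and 11% (CV 0.7). At log-SD 0.5 and CV 0.7 it is 10% and 16-18%. In a floor scenario (floor 50 AU/mL, 60% negatives in one group against 40% or 30% in the other, half of negatives not responding) it is 9% and 12%, against 22% and 32% for the pooled t-test.

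**The case against.** Four points deserve weight.

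- **A reader might infer that the primary test ignores baseline.** The documents do not support that. The outcome is an increase, and the secondary outcomes speak of change in titre, so baseline enters by subtraction or ratio. What is missing is adjustment for it. This stands.
- **The large error rates need two conditions together:** an increase in AU/mL and rises proportional to baseline. A t-test on each patient's fold rise, which the percentage hypotheses permit, shows no inflation when rises are proportional. This stands, and it is why the scale comes first in the fix. It does not clear the plan. The sizing is in AU/mL, and a log-fold t-test errs the other way when rises are independent of baseline (error 0-1%, so conservative in this direction).
- **Baseline is measured after three earlier doses.** It may partly be a result of the prior vaccine, and entry already selects on it. Conditioning on it can then remove part of a difference or introduce selection bias. The confounder label was written for cohort 2, where baseline precedes the randomised dose; carrying it over to cohort 3 is an inference. This stands as a limit on interpretation.
- **The cohort is exploratory and openly non-randomised.** That lowers the stakes. Even so, this is the cohort's stated primary comparison, with a formal alpha and power.

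**Conclusion.** The point holds in a limited form. The primary contrast of non-randomised groups has no baseline adjustment, and the scale of the increase is not fixed. If the increase is in AU/mL and rises are proportional to baseline, a modest imbalance raises one-sided error from 5% to 14-20% (ratio 1.25) or 25-41% (ratio 1.5). If rises do not depend on baseline, or fold rises are analysed under proportional rises, error is 5-6%.

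It would go too far to say that the planned test is biased, or to quote any of these rates as its actual error. The documents give no baseline titres by prior vaccine, no correlation between visits and no assay error, so the size and direction of any bias are unknown. The change should be made because it is cheap and because log-scale ANCOVA stays near 5% under both patterns of rise when assay error and floor values are absent. Confidence is medium.

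**What to change.** 1. State the scale of the increase: AU/mL difference, fold rise or log ratio.
2. Pre-specify baseline spike IgG as a covariate in the cohort 3 primary analysis. The preferred form is ANCOVA of log10 4-week IgG on prior-vaccine group and log10 baseline, reporting the adjusted geometric mean ratio with its confidence interval.
3. Name the initial-visit value as baseline, since patients are selected on a low earlier result. Pre-set the value used for results below the assay limit and repeat the analysis with another value.
4. Keep the planned t-test on the increase, in Welch form, as a sensitivity analysis. Welch is not itself a cure: in proportional scenarios with CV 1 (mean fold 3 or 4, 0% or 20% non-responders) its error was still 8-17% at ratio 1.5.
5. Describe the result as an association with prior vaccine conditional on baseline, not as a causal effect of switching.

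**Cost.** No new data are needed. The log version makes the effect a ratio, so the cohort 3 outcome wording and the sample-size sentence must be re-expressed. It can lose power if many patients sit at the assay floor, and floor values and assay error leave residual bias.

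The smaller change adds baseline as a covariate to the analysis of the AU/mL increase. It avoids the re-expression but corrects less. Under proportional rises, error is about 5-9% without assay error and 7-13% with log-SD 0.3 (CV 1). Power at equal baselines is 88-90%, against 97-98% for the log version (CV 0.7).

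The planned 80 should suffice. If 1000 AU/mL is the SD of the 4-week titre, adjustment at assumed baseline correlations of 0.3, 0.5 and 0.7 needs 21, 17 and 12 per group, against 22.

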Our target population consists of patients with a known diagnosis of cancer who were seen at the study site after Aug 1, 2021. Our study will employ the following inclusion criteria:

- Above the age of 18
- Meet one of the sub-criteria below:
 - Meet the CDC definition for immunocompromised status for cancer patients, i.e patients receiving active treatment for solid tumor or hematologic malignancy OR
 - Be a recipient of stem cell transplant or CAR-T cell therapy in the last 2 years OR
 - Have a negative SARS-CoV-2 spike IgG despite standard vaccination series, irrespective of active/inactive cancer status, on observation, or active therapy.
- Underwent an in-person encounter at a study facility during the study period
- Have received the second of the mRNA vaccines (BNT162b2 or mRNA 1273) or the adenoviral Ad26CoV2.S vaccine at least 28 days before the booster dose.

Exclusion Criteria

- Patients who have had a serious adverse reaction to any prior COVID-19 vaccines resulting in emergency room visit or hospitalization, had events related to myocarditis, thrombosis and thrombocytopenia syndrome or anaphylaxis to any prior dose of the COVID-19 vaccines.
- Patients who have had a documented COVID-19 infection in the 90 days prior to starting the study

Outcomes

We will be studying the following primary outcome:

- Rates of seroconversion for SARS-CoV-2 spike antibody after 4 weeks after a booster dose of BNT162b2/mRNA-1273 COVID Vaccine in patients that were initially seronegative after standard vaccine series

We will be studying the following secondary outcomes:

- Safety of booster dose of BNT162b2 and mRNA 1273 vaccines
- Correlation between malignancy type and prior treatment type and seroconversion
- Correlation between timing of most recent cancer-directed treatment and seroconversion
- Correlation between the total number of cancer-directed treatments received and seroconversion
- Differences between booster efficacy dependent on prior vaccine type (mRNA vs. adenoviral, BNT162b2 versus mRNA-1273)
- T cell responses at baseline and 4 weeks following vaccination
- Antigen neutralization assay results at baseline and 4 weeks following vaccination

Duration of sustained immunogenicity following vaccination in seropositive patients following our cohort for 24 months following booster vaccinations

Cohort 2

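### The Wald test named for every variable in the logistic model can miss strong predictors of non-response when a category has few or no responders

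*Combined protocol and SAP*

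**What the plan says.** The Statistical analysis section plans two kinds of analysis for the predictors of seroconversion.

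- **Malignancy associations.** It states that "associations between certain malignancies and the rates of seroconversion in our prospective single arm study will be measured by Fisher's exact" tests, or Cochran-Mantel-Haenszel tests when the analysis is stratified.
- **Adjusted model.** Seroconversion, recent medical treatment and "additional factors such as history of malignancy will be examined through a multivariate logistic" regression. Once interaction terms have been considered, "a Wald test will be used to consider the statistical significance of all included variables", at the 0.05 level.

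No likelihood-ratio, exact or penalised test is named for the model, and there is no rule for sparse categories. The covariates, their categories and the reference levels are not listed.

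These analyses serve the secondary outcomes. For cohort 1 they include "Correlation between malignancy type and prior treatment type and seroconversion", together with the timing of the most recent treatment and the number of treatments. Cohort 2 repeats the same list. Cohort 3 uses change in titre instead, so this model does not bear on it.

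**The concern.** The Wald test divides a coefficient by its standard error. When every patient in a category fails to respond, the maximum-likelihood coefficient has no finite value: the software stops at a large negative number with an enormous standard error, and their ratio is close to zero. The stronger the evidence of non-response, the less the test sees it. With one or two responders the test works again, but it remains conservative.

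This matters because the model is meant to show which cancers and treatments go with failure to respond, in a trial of patients chosen largely for poor response. A treatment class in which nobody seroconverted could be reported as having no significant adjusted association.

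**Working it through.** **The plan's nearest figure.** The documents give no sample-size figure for the logistic model. The closest is the cohort 1 subset size of about 26 for 80% power at 5% significance, 10% versus 30% (Sample size, Cohort 1).

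n = [(z_alpha·√(0.1·0.9) + z_0.80·√(0.3·0.7)) / 0.2]² gives 20 one-sided and 24 two-sided. The exact one-sided binomial first reaches 80% at n = 25 (power 80.7%). At n = 26 the exact power is 83.7%. So 26 is reproduced to within about two patients of the two-sided and exact versions. That figure concerns a one-sample test of one subset against 10%. It says nothing about comparing categories within a model.

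**Inputs from the plan.** Rates of 10% and 30%; subsets from "We anticipate cohort sizes of at least 26 per cohort"; cohort 1 total from "Our planned sample size of up to 250 will have ample power"; cohort 2 total up to 100.

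**Assumptions.** Category sizes of 5 to 26, rates of 5% and 40% where used, a single binary predictor, and a two-sided 0.05 level (the plan does not state sidedness). The total of 52 is two subsets of 26.

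**Formulas.** Let a of m respond in the category and r of n in the rest.

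- Wald: z = b/SE, with b = log[a/(m−a)] − log[r/(n−r)] and SE² = 1/a + 1/(m−a) + 1/r + 1/(n−r). At a = 0 both b and SE diverge.
- Likelihood ratio: 2[ℓ(a,m) + ℓ(r,n) − ℓ(a+r,m+n)], with ℓ(x,k) = x·log(x/k) + (k−x)·log((k−x)/k), referred to chi-square on 1 df.
- Firth: the same comparison after adding half the log determinant of the information matrix to the log-likelihood.

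**Zero responders, 0/10 versus 16/42.** ℓ(0,10) = 0, ℓ(16,42) = −27.91, ℓ(16,52) = −32.10, so the likelihood-ratio statistic is 8.37 and p = 0.004. Firth gives p = 0.015 and Fisher p = 0.022. Wald p is about 1. In fits with convergence settings like R's, at totals of 52, 100 and 250 and category sizes of 5 to 26, the coefficient stopped at about −15 to −19 with SE of about 1,000 to 4,000. Wald p was about 0.99 each time.

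**One responder, 1/15 versus 70/235.** b = −1.78, SE = 1.04, z = −1.71, Wald p = 0.088. The likelihood-ratio statistic is 4.74, p = 0.029. Firth p = 0.053.

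**Chance of no responders, (1 − rate)^m.** At 10%: 35% (m = 10), 21% (m = 15), 6% (m = 26). At 5%: 60%, 46%, 26%.

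**Power by exact enumeration** (a zero-responder category counted as not significant by Wald):

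| Category vs rest | Rates | Wald | Firth | Likelihood ratio |
|---|---|---|---|---|
| 26 vs 26 | 10% vs 30% | 35% | 44% | 47% |
| 26 vs 224 | 10% vs 30% | 50% | 64% | 69% |
| 15 vs 85 | 10% vs 30% | 4% | 35% | 45% |
| 10 vs 42 | 5% vs 40% | 4% | 64% | 77% |

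**Size, 10 vs 42 with 30% in both:** Wald 2.7%, Firth 4.4%, likelihood ratio 6.5%. Part of the likelihood-ratio advantage in small cells therefore comes from exceeding 5%. Firth is the fairer comparator.

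**Very small categories.** With 0/5 versus 30% in the rest (total 250), likelihood ratio gives p = 0.06, Firth 0.19 and Fisher 0.33. No test reaches 0.05, so the limit there is the sample and not the test.

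**The case against.** A reader might infer that the strongest predictors will be declared non-significant. The documents do not support that. Near-certain failure needs a modelled category with no responders at all, and no categories, counts or expected zeros are given. The one predefined grouping pools prior anti-CD20, CAR-T and stem cell transplant into a single subset, and timing and number of treatments need not be categorical. With one responder Wald can still reject: 1/26 against 30% in the rest (total 250) gives p = 0.022.

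A reader might also infer that the plan has no protection against zero cells. It has: Fisher's exact test is valid there, and 0/15 against 30% in the rest (total 250) gives p = 0.014. For malignancy type, this answers most of the concern. It does not answer it for prior treatment type, timing or number of treatments, to which those tests are not clearly extended. Nor does it supply the multivariable-adjusted result.

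The loss is also small in large groups: 50 versus 200 at 10% versus 30% gives Wald 87% and likelihood ratio 90%. The 4% against 64% contrast rests on a category of 10 and on rates of 5% and 40% that appear nowhere in the plan. Finally, these are secondary analyses in a study that calls itself exploratory, and Wald tests are ordinary practice where no category is sparse. All of this limits the weight of the point without removing it.

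**Conclusion.** The concern holds conditionally. Wald is the only test named for the model terms, it fails outright in a zero-responder category, and it loses power when responders are few. At the plan's own rates with a category of 26, the loss against Firth is 9 percentage points (26 versus 26) or 14 points (26 versus 224). With 15 versus 85 it is 31 points. These figures assume one binary predictor and a two-sided 0.05 level. How often a sparse category would arise cannot be determined from the documents. The primary endpoints, the sample sizes and the cohort 3 analysis are unaffected. This is an inexpensive improvement that should be made, not a flaw that undermines the trial.

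**What to change.** In the Statistical analysis section, replace the Wald test by Firth penalised logistic regression, with penalised-likelihood-ratio tests and profile-likelihood intervals for the model terms. Ordinary likelihood-ratio tests with profile intervals are acceptable where no category is sparse.

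The cost is one sentence. The plan already says that "statistical analysis will be done in the R software environment", where these methods are available, and no further patients or data are needed. The downside is slightly shrunken estimates. The change will not rescue categories of about five patients, which should be reported descriptively.
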